The primary hypothesis is that there is a better anesthetic stability in the deep NMB group (Group 2) and that this is translated as a reduction of the BIS signal variability and a reduction in the required effect-site concentrations of propofol and remifentanyl (representative of the total drug consumption).

b) Secondary objectives

As a secondary objective, we will study the quality of recovery using the PQRS scale to see if maintaining a deep NMB level during surgery has an impact on the patients' quality of recovery.

The secondary hypothesis is that the quality of recovery (PQRS test) is better in the patients of Group 2.

Can adequacy of anesthesia depth and quality of recovery be influenced by the level of neuromuscular blockade?

6. Study design

Patients subjected to anterior cervical spine surgery under general intravenous anesthesia will be randomized to receive one of two protocols regarding the neuromuscular blockade:

- Group 1 – Standard Clinical Practice Group - standard NMB, with a standard rocuronium dose for intubation (0.6 mg/kg). If required, the reversal of neuromuscular block is performed with neostigmine.
- Group 2 – Deep NMB group - with a standard rocuronium dose for intubation (0.6 mg/kg), followed by a constant infusion of rocuronium (10-15 µg/kg/min) to guarantee a PTC less or equal to 2 on the TOF monitor (PTC is evaluated every 5 minutes). The reversal of neuromuscular block is performed with Sugammadex (4 mg/kg).

a) Primary Endpoints

- BIS signal variability using the measured standard deviation during the maintenance phase of anesthesia
- Required effect-site concentrations of remifentanyl and propofol

b) Secondary Endpoints

- PQRS results at 15 and 40 minutes after surgery (taking into account the patient baseline values of the PQRS test done on the pre-anesthetic visit)
- PQRS results at day 3 after surgery

c) Study type

This is an interventional, phase 4, double-arm, parallel, randomized, open-label, single-center study aiming to compare two anesthesia protocols.

Can adequacy of anesthesia depth and quality of recovery be influenced by the level of neuromuscular blockade?

d) Study Timeline

- Study Start Date: April 2016
- Study End Date: April 2017
- First Patient In: April 2016
- Last Patient In: April 2017
- Last Patient Out: April 2017
- Study Analysis: May 2017
- Publication: November 2017

Can adequacy of anesthesia depth and quality of recovery be influenced by the level of neuromuscular blockade?

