e) Flow-chart

Assessment Title	Pre-anesthesia	Anesthesia procedure during surgery	15 minutes PQRS Test	40 minutes PQRS test	Follow-up
Assessment Number	Assessment 1	Assessment 2	Assessment 3	Assessment 4	Assessment 5
Scheduled Day	One the day before surgery	Day 1, time 1	Day 1, time 2: 15 minutes after surgery	Day 1, time 3: 40 minutes after surgery	3 days after surgery
Scheduling Window		>90 minutes	±5 minutes	±5 minutes	±1 days
Informed Consent	X				
PQRS test	X		X	X	X
Medical History	X				
Entry Criteria	X	X			
(Serious)Adverse Events	X	X	X	X	X
Physical Examination	X				
Patient Data online recording		X			
Patient randomization		X			
Patient Satisfaction evaluation					X
Dispense Trial Medication		X			
Pregnancy test	x				

Can adequacy of anesthesia depth and quality of recovery be influenced by the level of neuromuscular blockade?

f) Randomization and blinding procedures

This will be an interventional, randomized and unblinded study, performed at a single center (Centro Hospitalar do Porto).

Patient randomization will be done by a computer software programmed with a varying block randomization technique (to ensure sample size due to the small number of patients in each group), using a uniform distribution. The software will be installed in the data collection computer, and the anesthesiologist will only know to which group the patient was randomly assigned before induction starts. Although block randomization is used, the computer software does not display information about the block assignment of future patients to the user. The software is programmed using the Statistical toolbox of MATLAB.

g) Treatment

Trial participants will be randomly assigned (using varying block randomization) to one of two groups:

- Group 1 – Standard Clinical Practice Group - standard NMB, with a standard rocuronium dose for intubation (0.6 mg/kg). If required, the reversal of neuromuscular block is performed with neostigmine.
- Group 2 – Deep NMB group - with a standard rocuronium dose for intubation (0.6 mg/kg), followed by a constant infusion of rocuronium (10-15 µg/kg/min) to guarantee a PTC less or equal to 2 on the TOF monitor (PTC is evaluated every 5 minutes). The reversal of neuromuscular block is performed with Sugammadex (4 mg/kg).

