General anesthesia will be performed with total intravenous technique using the hypnotic propofol, the analgesic remifentanil and the neuromuscular relaxant rocuronium. Target controlled infusion (TCI) will be used for propofol and remifentanil. Standard routine anesthesia practice for these procedures uses total intravenous anesthesia with propofol and remifentanil by TCI and rocuronium. A single bolus dose of rocuronium is given for tracheal intubation

Can adequacy of anesthesia depth and quality of recovery be influenced by the level of neuromuscular blockade?

and no further doses are administered during the procedure. At the end of surgery, NMB is reversed only if TOF is below 90%

h) Treatment duration

Study treatment will be administered during surgery only, on day one.

i) Discontinuation criteria

A patient may request to discontinue from the clinical trial at any time for any reason.

The investigator in any case in which emerging effects are of unacceptable risk to the individual subject, will discontinue the patient from the study. In addition, the investigator will stop study for any patient with unmanageable factors that may interfere significantly with the trial procedures and/or the interpretation of results.

If the MAP does not respond to the protocol steps described in section 8, then the study should be stopped for that subject.

j) Investigational product accountability

These requirements apply only to Sugammadex, which is already commercialized in Portugal and is used in current clinical practice at the Centro Hospitalar do Porto.

The internal labeling will be performed by our pharmacy department according to GCP guidelines and the local regulations for clinical trials. All drugs used, except for Sugammadex, will be labelled according to standard practice.

Can adequacy of anesthesia depth and quality of recovery be influenced by the level of neuromuscular blockade?

The investigator will be responsible for the destruction of the supplies of Sugammadex at the study center pursuant to the GCP Guidelines, local regulations and the investigator's institutional policies.

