Clinical supplies of the drug Sugammadex will be received by a designated person of the pharmacy department at the site, handled and stored safely and properly, and kept in a secured location. Clinical supplies are dispensed in accordance with the protocol, i.e. the pharmacy will be informed of the patient randomization and the need for the use of Sugammadex in the beginning of the surgery and the drug will be sent to the operating room.

The investigator will keep accurate records of the clinical supplies and the amount dispensed for each patient assigned to Group 2.

k) Blinding and Un-blinding procedures

Not applicable.

l) Source documents and data collection

Part of data will be recorded electronically: Trial participants will be monitored with standard ASA monitoring. Additional monitoring (i.e. intra-arterial pressure) will be provided depending on patient clinical status. The monitoring equipment is as follows:

- TOF Watch SX monitor for neuromuscular block assessment
- BIS – Bispectral Index Monitor (Covidien)
- Aisys Anaesthesia Monitor (General Electrics - GE)
- Fresenius Orchestra Base Primea, with TCI for propofol and remifentanyl
- Syringe pump attached to the Fresenius Base Primea for the continuous infusion of rocuronium

Data collection software (Rugloop® Software and TOF Link) is installed on a Laptop computer connected to the Base Primea infusion pumps, the BIS monitor,

Can adequacy of anesthesia depth and quality of recovery be influenced by the level of neuromuscular blockade?

GE monitor and TOF Watch monitor, allowing for all data to be recorded online. The patient data files generated by the Rugloop® software will be accessed using the Labgrab® software and exported to excel files. TOF watch data will also be exported to excel files. All online data is posteriorly recorded in a patient individual CD.

All non-electronic data will be noted on the patients' paper CRF and on the RugLoop® software notes toolbar.

Can adequacy of anesthesia depth and quality of recovery be influenced by the level of neuromuscular blockade?

7. Selection and discontinuation criteria

a) Inclusion criteria

1. Patients ASA I-III
2. Between 18 – 80 years old
3. Scheduled for routine cervical surgery
4. Minimum duration of surgery is 90 minutes and performed with total intravenous anaesthesia (TIVA) with the hypnotic propofol, the analgesic remifentanyl and the neuromuscular relaxant rocuronium

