The day before surgery informed consent will be obtained and baseline PQRS test performed. Patients with neuromuscular diseases and severe cardiac and respiratory pathologies, or that have any contra indication for any of the drugs used, or that are not able to complete the baseline PQRS test will be excluded from the study.

i. Assessment 2

Assessment name: Anesthesia procedure during surgery

Timing: Day 1, time 1

Entry Criteria
(Serious) Adverse Events
Patient Data online recording
Patient randomization
Dispense Trial Medication

On the day of surgery, the patients will be randomly assigned (using varying block randomization) to one of two groups:

- Group 1 – Standard Clinical Practice Group - standard NMB, with a standard rocuronium dose for intubation (0.6 mg/kg). If required, the reversal of neuromuscular block is performed with neostigmine.
- Group 2 – Deep NMB group - with a standard rocuronium dose for intubation (0.6 mg/kg), followed by a constant infusion of rocuronium (10-

Can adequacy of anesthesia depth and quality of recovery be influenced by the level of neuromuscular blockade?

15 µg/kg/min) to guarantee a PTC less or equal to 2 on the TOF monitor (PTC is evaluated every 5 minutes). The reversal of neuromuscular block is performed with Sugammadex (4 mg/kg).

The Hospital Pharmacy is informed of the need or not of Sugammadex and sends the drug to the surgery room (since the surgery will not take less than 90 minutes, there is plenty of time for the drug to reach the surgery room). The hospital pharmacy department already agreed with this procedure.

The anesthesia induction and maintenance is performed with the same protocol in both groups with TCI of propofol and remifentanyl. During the procedure, the remifentanyl and propofol effect-site target concentrations is titrated to achieve and maintain a BIS value between [40-60], and alarms are activated on the monitor; the Mean Arterial Pressure (MAP) should be maintained between [-30% +30%] of the baseline patient value.

Upon arrival at the surgery room, all patients will be monitored with standard ASA monitoring. Additional monitoring (i.e. intra-arterial pressure) will be provided depending on patient clinical status. The monitoring equipment is as follows:

- TOF Watch SX monitor for neuromuscular block assessment
- BIS – Bispectral Index Monitor (Covidien)
- Aisys Anaesthesia Monitor (General Electrics - GE)
- Fresenius Orchestra Base Primea, with TCI for propofol and remifentanyl

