At the 3rd day after surgery a telephone contact is made to identify the occurrence of any Adverse Event (AE) (according to Good Clinical Practice (GCP) guidelines and pharmacovigilance directives), as well as to evaluate patient satisfaction using only the PQRS questions that address this issue. If at the 3rd day after surgery the patient is still in the hospital, than the contact is performed face to face by the investigator or designated researcher. The overall data acquisition for each patient ends at this point.

The occurrence of SAE and AE is noted on the specific forms on the patient individual CRF and acted accordingly to the GPC guidelines.

The individual patient data will be anonymized after the 3rd day contact.

iv. Discontinuation Visit

(Serious) Adverse Events
Patient Satisfaction evaluation

Can adequacy of anesthesia depth and quality of recovery be influenced by the level of neuromuscular blockade?

c) Compliance with study treatment

Protocol compliance will be monitored, including accurate prescription and administration of study treatment according to protocol.

Study treatment (IMP and NIMP) will be supplied and administered by medical personnel, so no compliance issues are expected to occur.

d) Concomitant and prohibited medication

Allowed concomitant medication and prohibited medication are those described by the SoPC of the IMP and NIMPs.

e) Expenses and benefits

Participants in the study are not expected to have additional expenses due to their study participation, since treatment and follow-up are similar to standard practice. Participants may benefit from the close monitoring due to study design.

Unscheduled visits travel expenses (until 3 days after discharge) will be reimbursed by the Sponsor (up to € 30) against expenditure presentation document).

Can adequacy of anesthesia depth and quality of recovery be influenced by the level of neuromuscular blockade?

9. Efficacy evaluation

a) Efficacy measure

A 25% reduction on the BIS variability (standard deviation) is considered clinically relevant.

b) Methods

All hemodynamic and brain monitoring, TOF monitoring, and infusion pumps data will be recorded online during surgery with a sample time of 5 seconds, using data collection software on a laptop connected to all monitors and infusion pumps.

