Patients' data during surgery will be recorded on a research laptop with a code generator, which protects patient anonymity by generating a code for each individual patient.

All paper records (CRF) with the PQRS test results at the different time points will use the designated individual patient code. The patient CRF's will be kept on a secure archive cabinet during the duration of the study. The electronic data files

Can adequacy of anesthesia depth and quality of recovery be influenced by the level of neuromuscular blockade?

will be kept on the research laptop (with restricted permissions) and each patient will also have its own individual data CD.

Can adequacy of anesthesia depth and quality of recovery be influenced by the level of neuromuscular blockade?

15. Data handling record keeping

Clinical trial data will be maintained in the Case Report Form developed for the trial. All hemodynamic and brain monitoring, TOF monitoring, and infusion pumps data will be recorded on the hospitals computers. PQRS paper questionnaires will be filled out by the trial participants and kept in the participant's clinical chart.

Remaining source documentation is to be maintained as part of the participant's clinical chart. Deviations from this documentation method will be documented.

All data are to be attributable, legible, contemporaneous, original and accurate.

Can adequacy of anesthesia depth and quality of recovery be influenced by the level of neuromuscular blockade?

16. Financing and insurance

The study received a grant from Merck Sharp & Dohme and IMP (sugammadex) will be supplied by Merck Sharp & Dohme.

The study was designed and will be conducted, analyzed and interpreted by the investigator according to publications policy.

A clinical trial insurance for the trial participants and the investigators will be contracted by the study Sponsor.

Can adequacy of anesthesia depth and quality of recovery be influenced by the level of neuromuscular blockade?

17. Publication policy

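### The trial is declared fully unblinded although the group could be kept from the patient, which leaves the self-reported recovery outcomes exposed to avoidable expectation bias

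*Combined protocol and SAP*

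**What the plan says.** Section 6 f) of the combined protocol and SAP says: "This will be an interventional, randomized and unblinded study". Section 6 c) describes a "double-arm, parallel, randomized, open-label, single-center study aiming to compare two anesthesia protocols". Under the heading "k) Blinding and Un-blinding procedures" the only entry is that it does not apply. No reason is given for leaving the patient unblinded.

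On who learns the group, section 6 f) says that "the anesthesiologist will only know to which group the patient was randomly assigned before induction starts". It does not say whether the patient is told. On timing, Assessment 2 in section 8 b) says "On the day of surgery, the patients will be randomly assigned", and section 6 h) says "Study treatment will be administered during surgery only, on day one".

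On the outcomes, section 15 says "PQRS paper questionnaires will be filled out by the trial participants". For the day-3 contact, Assessment 5 in section 8 b) restricts the questions to the PQRS satisfaction items. The contact is by telephone or, if the patient is still in hospital, "performed face to face by the investigator or designated researcher". Nobody is named as giving the PQRS at 15 and 40 minutes.

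**The concern.** An open-label design is a reasonable choice when the treatment cannot be hidden. Here it cannot be hidden from the anesthesiologist, but it can be from the patient, who is unconscious when the arms begin to differ. The plan gives up both kinds of blinding together.

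Section 5 b) makes quality of recovery the whole secondary objective and predicts that Group 2 will do better. Section 17 plans two papers, one of them on that objective. If patients know their group and expect the deep-block strategy to be better, they may rate recovery and satisfaction more favourably. An assessor who knows the group may do the same when conducting or scoring items. A difference in favour of Group 2 could then not be separated from expectation, and none of the methods in section 11 could separate it afterwards.

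**Working it through.** The plan gives no effect size or SD for the PQRS, and section 11 b) explicitly leaves it out of the sample size calculation. There is no figure to reproduce, so the check is mainly a comparison of sections.

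**1. Could the patient be kept unaware?**
- Section 8 b), Anesthesia Protocol: induction, the loss-of-consciousness check and the rocuronium intubating dose are common to both groups. The group-specific rocuronium regimen begins after intubation.
- The same section places the group-specific reversal at the end of surgery, after the dressing, when propofol is stopped.
- Section 6 h): study treatment is confined to surgery.

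The patient is therefore not awake to see the arms diverge. Keeping the group from the patient is feasible without changing treatment.

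**2. When could an awake patient find out?**
- Section 6 f): the anesthesiologist learns the group before induction, while the patient is awake. There is no instruction not to disclose it.
- Section 6 e) (flow-chart) and Assessment 2 put randomization on the day of surgery. The item list for Assessment 1, the day before surgery, also includes patient randomization. These conflict. If the earlier timing were followed, the window for disclosure would be longer.
- After surgery, nothing prevents disclosure before the 15-minute, 40-minute or day-3 assessments.

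**3. Which outcomes are exposed?**
- Most exposed: the PQRS items that patients rate themselves, and all of the day-3 contact, which is satisfaction only. Day 3 is a listed secondary endpoint in section 6 b).
- Less exposed to patient expectation: the physiological and cognitive parts of the PQRS (section 4 describes a multi-domain scale). These depend more on how the assessor conducts and scores them.
- Not reached by this point: BIS variability and effect-site concentrations, which are recorded from monitors and pumps during anesthesia (section 9 b).

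**4. How sensitive is a comparison of this size?**
This is an illustration on assumptions that are not in the documents: one continuous score, no true effect, a two-sided test at 0.05, normal approximation, and a systematic shift of b standard deviations in one group. The group size of n = 35 is from section 11 b).

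Standardized shift: δ = b / √(2/n) = b / √(2/35) = b / 0.239.

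False-positive rate = 1 − Φ(1.96 − δ) + Φ(−1.96 − δ).

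| Assumed shift b (SD) | δ | False-positive rate |
|---|---|---|
| 0 | 0 | 5% |
| 0.1 | 0.42 | 7% |
| 0.2 | 0.84 | 13% |
| 0.3 | 1.26 | 24% |
| 0.5 | 2.09 | 55% |

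Section 11 a) also plans chi-square, Fisher and Cochran-Mantel-Haenszel tests on recovery proportions, to which these rates do not apply directly. In a score that mixes self-rated and measured items, the shift would be diluted.

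**The case against.** The strongest reply is that the documents never say patients learn their group. Only the anesthesiologist is said to be told, and a patient who is unconscious when the arms diverge may never find out. The consent pages are not available, so what patients are told about sugammadex is unknown. Section 6 j) says the drug is already in current use at the hospital, so an expectation that a novel drug is better cannot be taken for granted. All of this stands. A reader might infer from the unblinded label that the PQRS results will be biased. The documents support only a risk, in an assumed direction.

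A reader might also treat the PQRS as wholly patient-reported. It is not: section 4 includes physiological and cognitive domains, so telling patients nothing protects only part of the scale, and the assessor's knowledge may matter as much.

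Finally, it is tempting to say that the bias could be removed at no cost. That goes too far. Non-disclosure needs an instruction that staff follow. A separate assessor needs some organisation. The designated researcher is mentioned only for the day-3 contact and adverse event monitoring (sections 8 b and 10), not for the tests at 15 and 40 minutes. Neither measure guarantees that the group stays hidden.

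What the reply does not answer is that the plan declares the trial unblinded for everyone, gives no reason, and contains no instruction to withhold the group from the patient where this is feasible.

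**Conclusion.** The concern holds as an avoidable exposure to bias in the self-reported part of the secondary endpoint: the participant-completed PQRS items and the day-3 satisfaction contact. It rests on two facts in the plan (the arms diverge only under anesthesia, and no concealment from the patient is specified) and one assumption (that some patients would learn their group and respond to it). The size is unknown. The table above shows only that, at 35 per group, even modest systematic shifts would matter.

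The point does not extend to the primary endpoints. The open-label anesthesiologist who titrates propofol and remifentanil is a separate and harder problem, which this change does not touch. The change is worth making because it replaces an unexplained design choice with one less open to bias and leaves treatment, visits and sample size as they are.

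**What to change.** In section 6 f) replace the statement that the study is unblinded, and in section 6 k) replace the not-applicable entry, with: *The patient will not be told the assigned group, from randomization until the day-3 contact is complete, unless disclosure is needed for the patient's care or for safety reporting. The anesthesiologist will know the group.* Align the study-type wording in section 6 c) and the trial design entry in the synopsis.

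Add that, where existing staff allow, the person who gives the PQRS at 15 and 40 minutes and makes the day-3 contact is not the anesthesiologist of that case and does not consult the anesthesia record beforehand. Drop this part if it would need extra staff.

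Reconcile the Assessment 1 list in section 8 b), which includes patient randomization, with the flow-chart and the Assessment 2 text, which place it on the day of surgery.

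Cost: a protocol wording change, possibly a matching line in the patient information, and a small procedural burden on staff. The number of patients stays at 35 per group. Bias would be reduced, not eliminated.
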